Treatment of anemia of chronic disease with true iron deficiency in pregnancy

[name], [name], [name], [name]

Department of Obstetrics and Gynecology

University Hospital of Zurich

[name]

[name]

SWITZERLAND

[contact]

Email: [contact]

Study population and criteria

Fifty anemic pregnant women with moderate anemia were prospectively observed and treated in the Anemia clinic at the Department of Obstetrics, University Hospital Zurich. All patients had singleton pregnancies. All pregnant women fulfilled criteria of moderate iron deficiency anemia defined as hemoglobin between 8.0 and 9.9 g/dl and serum ferritin $<15 \mu\text{g/l}$. In all women, the analyses of a blood count, iron status, erythropoietin, cross reactive protein (CRP), folic acid and vitamin B₁₂ were conducted.

Primary endpoint was the assessment and comparison of the efficacy of anemia treatment in pregnant women with iron deficiency anemia and anemia of chronic disease with true iron deficiency.

Secondary endpoint was the target hemoglobin $\geq 10.5 \text{ g/dl}$.

Exclusion criteria were anemia of other etiology (i.e. vitamin B₁₂ deficiency, folic acid deficiency, hemoglobinopathy etc.), liver or kidney disease, and multiples. Women with mean corpuscular hemoglobin (MCH) $\leq 25 \text{ pg}$, mean corpuscular volume (MCV) $\leq 75 \text{ fl}$; and percentage of microcytic erythrocytes (MRC) $\geq 3\%$ were tested for hemoglobinopathies.

Flow cytometry was used to determine the total iron demand of erythropoiesis by measuring HRC, C_{HR}, and RDW. Iron deficiency anemia is defined as anemia with depleted iron stores and with elevated levels of HRC $>2.5\%$, decreased C_{HR} $<28 \text{ pg}$ and elevated RDW $>15\%$. In combination with the indicators of erythropoiesis (hemoglobin, red blood cells and hematocrit) as well as the indicators of iron household (serum ferritin and transferrin saturation), we identified anemia of chronic disease with reduced iron stores but with normal level of hypochromic erythrocytes (HRC $<2.5\%$), normal reticulocyte hemoglobin content (C_{HR} $>28 \text{ pg}$), normal red blood cell distribution width (RDW $<15\%$) and low serum EPO levels for the grade of anemia (serum EPO $<50 \text{ U/l}$ by Hb $<10 \text{ g/dl}$).

Laboratory assessment

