Hb, red blood cells (RBC), hematocrit (HCT), MCV, MRC, HRC, RDW, CHr were measured using an ADVIA® hematology analyser system (Bayer Diagnostics, Leverkusen, Germany). MCH was automatically calculated from Hb and RBC. Iron status was assessed by chemiluminescence-immunoassay (ACS 190; Ciba/Corning Diagnostic Corp., Cleveland, OH) of serum ferritin, iron and transferrin. Transferrin saturation was calculated as $100 \times \text{iron}/2 \times \text{transferrin}$. Radioimmunoassay was performed to determine vitamin B₁₂, folic acid and the levels of serum EPO. CRP was assessed through immunoturbidimetry. The hematological parameters were checked twice a week in the anemia clinic and iron status once a week.

Therapy protocol

According to hemoglobin level at the start of the therapy, the women were either treated with intravenous iron and rhEPO or with intravenous iron only twice weekly as described elsewhere. Patients with an Hb level between 9.0 and 9.9 g/dl (33 patients) received 200 mg iron sucrose (VENOFER®, Vifor Int., St. Gallen, Switzerland) intravenously twice weekly. If response to therapy was poor (i.e. Hb increase <0.7 g/dl) after 2 weeks (13 patients), patients additionally received rhEPO (10,000 U EPREX®, Janssen-Cilag, Baar, Switzerland). This cut-off for adequate primary response we choose on the basis of our previous experience. Patients with an Hb between 8.0 and 8.9 g/dl (17 patients) received iron sucrose (Venofer) and rhEPO (Eprex) twice weekly from the start of therapy.

Sufficient overall response to therapy (the difference of baseline hemoglobin and after therapy) was defined as Hb increase >1.0 g/dl. The maximum total iron dose was 1,600 mg, therefore therapy was stopped if the maximal iron sucrose dose was administered, or target Hb > 10.5 g/dl was achieved.

Side-effects (hypotensive and hypertensive response, allergic reaction, thromboembolic complications) were registered.

Statistical analysis

All statistical analyses were performed using the statistic program STATA 8 (Stata Corporation College Station, TX). $P<0.05$ was considered statistically significant. Baseline characteristics were compared using Mann-Whitney and Chi-square tests when appropriate.

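### The primary IDA versus ACD comparison has no stated analysis, and the only tests named cannot adjust for baseline Hb, which sets the starting regimen and strongly influences the rise

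*Combined protocol and SAP*

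**What the plan says.** Under Study population and criteria: "Primary endpoint was the assessment and comparison of the efficacy of anemia treatment in pregnant women with iron deficiency anemia", set against women who have anemia of chronic disease with true iron deficiency. No outcome variable or reading time is attached. A further aim follows: "Secondary endpoint was the target hemoglobin", given there as at least 10.5 g/dl.

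Under Laboratory assessment: "The hematological parameters were checked twice a week in the anemia clinic".

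Under Therapy protocol, the starting regimen depends on Hb: "According to hemoglobin level at the start of the therapy, the women were either treated with intravenous iron and rhEPO", or with iron alone. The 33 women at 9.0-9.9 g/dl start on iron alone and the 17 at 8.0-8.9 start on iron plus rhEPO. A later change depends on response: "If response to therapy was poor (i.e. Hb increase <0.7 g/dl) after 2 weeks (13 patients), patients additionally received rhEPO". Sufficient overall response is a rise of more than 1.0 g/dl. The end of treatment is also tied to Hb: "therapy was stopped if the maximal iron sucrose dose was administered, or target Hb > 10.5 g/dl was achieved", with the iron maximum at 1,600 mg.

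The Statistical analysis section covers three things: the software, the 0.05 significance level, and this: "Baseline characteristics were compared using Mann-Whitney and Chi-square tests when appropriate".

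**The concern.** The main question has no planned analysis. The only tests in the plan are assigned to baseline characteristics, and in the form named neither takes a covariate. That diagnosis is not randomised is inherent to the question and is not the fault. The fault is that nothing is said about the one variable that the protocol builds into both treatment and outcome.

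Baseline Hb enters in two ways. It decides who receives rhEPO from the start. And because treatment stops at a fixed Hb while response is a change from baseline, a woman who starts low and reaches the target must show a large rise, and one who starts high may show only a small one. Reaching the target works the other way, since it is easier from a higher start.

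If IDA and ACD women differ in baseline Hb, an unadjusted contrast can show an efficacy difference that reflects starting Hb and starting regimen. Independence of diagnosis and baseline Hb cannot be assumed, because hemoglobin is among the markers used to identify ACD: "In combination with the indicators of erythropoiesis (hemoglobin, red blood cells and hematocrit) as well as the indicators of iron household". No Hb cut-off by diagnosis is given, however.

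**Working it through.** **Figures from the documents.** 17 + 33 = 50, which matches the stated number of women. There is no power calculation to reproduce. The documents give neither the IDA/ACD split nor baseline Hb by diagnosis.

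**Rise at the stop.** Rise = stopping Hb minus baseline Hb. Take 10.6 g/dl as the first value above 10.5. This is a treatment stop, not a ceiling on Hb.
- From 8.0-8.9: 10.6 - 8.9 = 1.7 to 10.6 - 8.0 = 2.6, always a responder.
- From 9.6-9.9: 10.6 - 9.9 = 0.7 to 10.6 - 9.6 = 1.0, not a responder although the target was reached.

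**Weekly rate needed to reach 10.6.** If 200 mg per infusion applies to all women (it is written only for the 9.0-9.9 group), 1,600 / 200 = 8 infusions, about 4 weeks.
- From 8.0-8.9: 1.7 / 4 = 0.43 to 2.6 / 4 = 0.65 g/dl per week.
- From 9.0-9.9: 0.7 / 4 = 0.18 to 1.6 / 4 = 0.40 g/dl per week.

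At a common rate of rise, lower baseline Hb therefore favours the change measure and hinders the target measure.

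**Simulation, no true diagnosis effect.** Assumptions: 20 ACD and 30 IDA women; exactly 17 at 8.0-8.9; twice-weekly readings; stop above 10.5 or after 8 infusions; rhEPO added at 2 weeks if the rise is below 0.7; between-woman SD 0.15 and reading SD 0.2. The iron rate is set at 0.37 g/dl per week so that add-ons average the reported 13. The iron plus rhEPO rate runs from 0.37 (no gain) to 0.70. There were 2,000-4,000 runs per setting.

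| Low starters, ACD of 20 / IDA of 30 | Gap (points) | Type I error, unadjusted Mann-Whitney on Hb change |
|---|---|---|
| 6/11, 7/10, 8/9 | 2-10 | 0-5% |
| 5/12, 9/8 | 15-18 | 3-8% |
| 4/13, 10/7 | 23-27 | 6-24% |
| 3/14, 11/6 | 32-35 | 9-53% |

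A linear model adjusted for baseline Hb gives 3-6%, with bias of at most 0.02 g/dl.

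**Binary measures at 32-35 points.** For target Hb with no rhEPO gain, chi-square gives 21-23% and Mantel-Haenszel 4-5%. For response above 1.0 g/dl, chi-square gives 6-12% and Mantel-Haenszel 4-6%.

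**Does the baseline comparison protect?** A Mann-Whitney test of baseline Hb reaches p<0.05 in 16-25% of trials at 23-27 points and 43-62% at 32-35. Chi-square on the starting strata misses both middle cases. For 10/20 v 7/30, the pooled share is 17/50 = 0.34 and z = 0.267 / sqrt(0.34 x 0.66 x (1/20 + 1/30)) = 1.95, so p = 0.051. For 4/20 v 13/30, p = 0.088.

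**How likely is such a gap by chance?** Drawing the 17 low starters at random (hypergeometric, 20/30 split), a gap of at least 23 points has probability 13% and one of at least 30 points 3%.

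**Power when diagnosis is unrelated to baseline Hb.** For a rise 0.10 g/dl per week slower in ACD: 20-40% adjusted against 8-31% unadjusted. For 0.20: 74-94% against 30-87%.

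**Robustness.**
- SDs of 0.10-0.25 between women and 0.2-0.3 for readings: 5-24% at 23-27 points, 8-56% at 32-35, adjusted 3-7%.
- Final Hb read one week after the stop, with the rise continuing at half rate: 8-22% and 10-51%, adjusted 3-7%.
- Splits 15/35 and 25/25: 7-29% at 28-30 points, adjusted 2-7%.
- A simpler model (25/25 split, 60-100% of women reaching the target, low starters 12 v 5): spurious difference in mean rise 0.22-0.27 g/dl, Mann-Whitney 13.5-28%, adjusted 4.2-5.2%. With low starters 10 v 7, no test clearly exceeds 5%.

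**The case against.** The documents support a primary analysis left unspecified, not an unadjusted analysis planned. The inflated error rates belong to a test and a variable that the plan never joins together, and they depend on an imbalance that no section reports. Averaged over random splits, the unadjusted Mann-Whitney test holds 4.4-5.1%, so expected inflation is nil unless diagnosis and baseline Hb are associated. The case for an association is thin: the features that separate ACD from IDA are the red-cell indices and EPO, and every woman has Hb of 8.0-9.9. The 53% needs both the widest gap and the largest assumed rhEPO gain. A false positive that the baseline test also fails to flag is rarer: 4-10% at 23-27 points and 2-11% at 35. The opposite pull of the two measures also depends on the unknown rhEPO effect: target attainment in the low v high stratum moves from 21% v 77% with no gain to 87% v 92% at 0.70. Matching the iron rate to 13 add-ons depends on coding detail as well; another coding needs about 0.39.

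Most of this stands as a limit on size, and 53% should not be read as the expected harm. It does not remove the point. The primary comparison still has no analysis, a baseline test that flags a gap does not correct for it, and the power gain from adjustment appears without any imbalance.

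**Conclusion.** The concern holds and should be fixed; confidence in its size is medium. Two parts rest on the text alone: no analysis is stated for the primary comparison, and baseline Hb sets the starting regimen and, through the fixed stop, strongly influences the rise. The size is conditional on assumed rates and SDs, the group split and an unadjusted test being used. Gaps up to about 18 points do little harm (at most 8%). At 23-27 points the worse of the two measures, Hb change or target Hb, has 10-24% type I error at each rate tested, and at 32-35 points 16-53%. Whether any such gap exists cannot be told from the documents. With balanced groups the unadjusted test is valid but conservative, and the loss is in power.

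**What to change.** Add one paragraph to Statistical analysis:

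- Analyse Hb change from baseline to end of therapy with a linear model on diagnosis and continuous baseline Hb, and report the adjusted difference with its 95% CI. State when the end-of-therapy Hb is read.
- Compare response above 1.0 g/dl and target Hb by diagnosis, stratified at 9.0 g/dl (exact or Mantel-Haenszel). The target is at least 10.5 in one section and above 10.5 in another; the two must be reconciled.
- Do not adjust for the rhEPO add-on, because it follows response.
- Report baseline Hb, starting regimen and add-on by diagnosis.
- As a sensitivity analysis, give the baseline-adjusted 2-week Hb change in the 33 women at 9.0-9.9, using the last reading for anyone who stopped earlier. Under the same assumptions its type I error is 4-6%, with power 29-31% for 0.10 and 81-83% for 0.20 g/dl per week.
- If outcome data have been seen, label the adjusted analysis as not pre-specified.

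The cost is one model degree of freedom and no new data: baseline Hb is known for all 50 women and Hb was read twice weekly. Some limits remain. Pre-specification cannot be restored, adjustment cannot separate rhEPO from baseline Hb, and a 95% CI half-width of about 0.15-0.26 g/dl leaves low power for a small difference.
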